10.6 Required Routine Reporting

10.61 Baseline and Adverse Events Evaluations

Pretreatment symptoms/conditions to be graded at baseline and adverse events to be graded at each evaluation.

Grading is per CTCAE v5.0 **unless** alternate grading is indicated in the table below:

CTCAE System/Organ/Class (SOC)	Adverse event/Symptoms	Baseline	Each evaluation
Investigations	Platelet count decreased*	X	X
Blood and lymphatic system disorders	Anemia*	X	X
Cardiac disorders	Atrial Fibrillation	X	X
General disorders and administrative site conditions	Fatigue	X	X
	General disorders and administrative site conditions – other, hemorrhage ¹	X	X
Injury, poisoning and procedural complications	Infusion related reaction	X	
	Bruising	X	X
Skin and subcutaneous tissue disorders	Rash maculo-papular	X	X
Musculoskeletal and connective tissue disorders	Arthralgia	X	X
Vascular disorders	Hypertension	X	X

* Grading will be performed by the study statisticians at the time of analysis based on the CLL toxicity grading scale for blood counts in Appendix V. CTCAE grades for platelet count decreased and anemia will also be recorded for reporting purposes.

¹Includes hemorrhages of all systems.

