10.62 All other AEs

Submit via appropriate MCCC Case Report Forms (i.e., paper or electronic, as applicable) the following AEs experienced by a patient and not specified in Section 10.6:

10.621 Grade 2 AEs deemed *possibly, probably, or definitely* related to the study treatment or procedure.

10.622 Grade 3 and 4 AEs regardless of attribution to the study treatment or procedure.

10.623 Grade 5 AEs (Deaths)

10.6231 Any death within 30 days of the patient's last study treatment or procedure regardless of attribution to the study treatment or procedure.

10.6232 Any death more than 30 days after the patient's last study treatment or procedure that is felt to be at least possibly treatment related must also be submitted as a Grade 5 AE, with a CTCAE type and attribution assigned.

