10.87 Maintenance of Safety information

All safety data should be maintained in a clinical database in a retrievable format. The PRINCIPAL INVESTIGATOR shall provide all adverse events, both serious and non-serious, in report format. However, in certain circumstances more frequent provision of safety data may be necessary, e.g. to fulfill a regulatory request, and as such the data shall be made available within a reasonable timeframe at J&J request.

10.88 Procedures for Reporting Safety Data and Product Quality Complaints (PQCs) for Janssen Medicinal Products to J&J

All adverse events and special situations, whether serious or non-serious, related or not related, following exposure to a J&J medicinal product are to be documented by the investigator and recorded in the CRF and in the subject's source records. Investigators must record in the CRF their opinion concerning the relationship of the adverse event to a J&J medicinal product.

All (serious and non-serious) adverse events reported for a J&J medicinal product should be followed up in accordance with clinical practice.

10.89a SAEs, AEs of Special Interest and Special Reporting Situations

All serious adverse events that have not resolved by the end of the study, or that have not resolved upon discontinuation of the subject's participation in the study, must be followed until any of the following occurs:

1. The event resolves
2. The event stabilizes
3. The event returns to baseline, if a baseline value/status is available
4. The event can be attributed to agents other than the study drug or to factors unrelated to study conduct
5. It becomes unlikely that any additional information can be obtained (subject or health care practitioner refusal to provide additional information, lost to follow-up after demonstration of due diligence with follow-up efforts)
6. The PRINCIPAL INVESTIGATOR will transmit all SAEs, AESIs and special situations following exposure to a Janssen product under study in a form provided by J&J in accordance with Section 16, Transmission Methods, in English within 3 business days of becoming aware of the event(s).
7. All follow-up information for serious adverse events that are not resolved at the end of the study or by the time of patient withdrawal must be reported directly by the PRINCIPAL INVESTIGATOR, within 3 business days becoming aware, to J&J using the J&J Serious Adverse Event Report

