16.322 The MRD response rate at any time during the course of treatment with daratumumab plus ibrutinib will be estimated by the number of patients who achieve MRD negative response in both blood and bone marrow at any time during combination treatment divided by the total number of evaluable patients. Exact binomial 95% confidence intervals for the true success rate will be calculated. In patients who achieve MRD negative response, time to achieve MRD negative response will be summarized descriptively (median, range). Time to achieve MRD negative response is defined as time from registration to the earliest date of documentation of MRD negative response in both blood and bone marrow.

16.323 Progression-free survival is defined as the time from registration to the earliest date of documentation of disease progression or death due to any cause. Patients who receive subsequent treatment for CLL before disease progression will be censored on the date of their last disease assessment prior to initiation of the subsequent treatment. The distribution of progression-free survival will be

estimated using the method of Kaplan-Meier.

16.324 Adverse Events: Platelets and hemoglobin will be graded according to the Grading Scale for Hematologic Adverse Events in CLL Studies in Appendix V. The maximum grade for each type of adverse event, regardless of causality, will be recorded and reported for each patient, and frequency tables will be reviewed to determine adverse event patterns. Adverse events will continue to be recorded and reported up to 30 days after the last day of study drug treatment.

16.34 Over Accrual: If more than the target number of patients are accrued, then the additional patients will not be used to evaluate the stopping rule or used in any decision making processes; however, they will be included in final point estimates and confidence intervals.

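### Sections 10.62 and 10.82/10.88 set conflicting rules for which adverse events reach the case report forms; if 10.62 alone is applied, the all-cause summary in 16.324 could understate low-grade toxicity for unsolicited terms

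*Combined protocol and SAP*

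**What the plan says.** Section 16.324 describes the analysis: "The maximum grade for each type of adverse event, regardless of causality, will be recorded and reported for each patient". It sets no minimum grade and does not say which collection rule supplies the data.

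Three places govern collection.

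- **Section 10.61** lists ten solicited terms and asks for "Pretreatment symptoms/conditions to be graded at baseline and adverse events to be graded at each evaluation". It applies no filter by attribution or grade. Diarrhea and nausea are not on the list.
- **Section 10.62** tells staff what else to submit on the cancer center's case report forms: "the following AEs experienced by a patient and not specified in Section 10.6" (read here as 10.61, since 10.62 is itself part of 10.6). The items are "Grade 2 AEs deemed *possibly, probably, or definitely* related to the study treatment or procedure"; "Grade 3 and 4 AEs regardless of attribution to the study treatment or procedure"; and deaths, starting with "Any death within 30 days of the patient's last study treatment or procedure regardless of attribution to the study treatment or procedure" and adding later deaths thought at least possibly related to treatment. Grade 1 events and unrelated Grade 2 events do not appear.
- **Sections 10.82 and 10.88** set a wider rule. Section 10.82 covers all adverse events for the manufacturer's products whatever the cause, and names both daratumumab and ibrutinib as such products. Section 10.88 says that events, "whether serious or non-serious, related or not related, following exposure to a J&J medicinal product are to be documented by the investigator", and that they go into the case report form as well as the source records. Neither section gives a grade threshold.

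**The concern.** Staff who take 10.62 as their data-entry rule would not enter Grade 1 events or unrelated Grade 2 events for any term outside the solicited list. A summary built from those forms would be all-cause for solicited terms and for Grade 3 and above, but filtered by investigator attribution for unsolicited Grade 2. Nothing in 16.324 would tell a reader so.

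The toxicity profile is a secondary goal in both cohorts (Sections 2.24 and 2.28), and Section 16.23 counts toxicity among the factors in any decision to terminate. There is no control arm. Section 1.3 says that daratumumab has not been studied clinically in CLL, so attribution rests on little experience in this disease. These are the reasons for choosing an all-cause summary, and an unstated relatedness filter would work against it.

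**Working it through.** The plan states no figure on this point, so there is none to reproduce. The check is a comparison of the rules, followed by a rough scale.

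**Step 1: the rules side by side.**

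| Event | Under 10.61/10.62 | Under 10.82/10.88 | Within the scope of 16.324 |
|---|---|---|---|
| Solicited term, any grade or attribution | entered | entered | yes |
| Unsolicited, Grade 1 | not listed | entered | not excluded (no minimum grade) |
| Unsolicited, Grade 2, at least possibly related | entered | entered | yes |
| Unsolicited, Grade 2, unlikely or unrelated | not listed | entered | yes |
| Unsolicited, Grade 3-4, any attribution | entered | entered | yes |
| Death within 30 days of last treatment | entered | entered | yes |

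The rules differ in two rows. The unrelated Grade 2 row conflicts directly with the causality wording of 16.324. The Grade 1 row is a conflict between 10.62 and 10.88; 16.324 neither promises nor excludes Grade 1.

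**Step 2: scale if 10.62 alone governed.**

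Inputs from the ibrutinib safety paragraph in Section 1.2 (monotherapy, n=506):

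- diarrhea: 42.1% all-cause, 30.2% related
- nausea: 26.1% all-cause, 15.0% related

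Inputs from Section 16.12: maximum accrual 52; 22 evaluable patients in Cohort 1 and 26 in Cohort 2.

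Assumptions: these rates carry over to this trial; the all-cause and related rates share one denominator; every unrelated event is Grade 2 or lower. The last is plausible for these two terms, because Section 1.2 describes gastrointestinal events as rarely severe, with few at Grade 3 and none at Grade 4.

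Formulas: patients lost to the relatedness filter = (all-cause rate − related rate) × N; share of cases lost = 1 − related rate / all-cause rate.

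- Diarrhea: 0.421 − 0.302 = 0.119. With N = 52, 21.9 patients fall to 15.7, a loss of 6.2. Share lost: 1 − 0.302/0.421 = 28.3%. By cohort: 0.119 × 22 = 2.6 and 0.119 × 26 = 3.1.
- Nausea: 0.261 − 0.150 = 0.111. With N = 52, 13.6 patients fall to 7.8, a loss of 5.8. Share lost: 1 − 0.150/0.261 = 42.5%. By cohort: 0.111 × 22 = 2.4 and 0.111 × 26 = 2.9.

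**Step 3: range.** If 10.82/10.88 is followed, the loss is 0. If 10.62 alone is followed, it is about 6 of 52 for each term. It would be less if some unrelated events reach Grade 3, and more by however many related events are Grade 1. The documents give no grade split from which to size that last part.

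**The case against.** The strongest reply is that nothing need be lost. Section 10.8 is headed as additional instructions, so it can be read as supplementing 10.62. Section 10.62 lists what to submit but does not say that only those events may be entered. Staff who follow the whole protocol would record everything, and 16.324 agrees with that wider rule. Section 18.1 also refers to a separate Data Submission Schedule, not included here, which may settle the matter. This stands as far as it goes: it makes the loss conditional and its lower limit zero. It does not remove the conflict. Section 10.62 sits under required routine reporting and names the trial's own forms, while 10.88 sits among the manufacturer's instructions, so staff could reasonably treat either as the governing rule.

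A reader might go on to infer that the summary will understate toxicity. The documents do not support this, because 10.82 and 10.88 call for exactly the events that 10.62 leaves out.

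A reader might also take the pooled rates elsewhere in Section 1.2 (diarrhea 35.9%, nausea 20.2%, cough 17.5%, N=1061) as the amount missing. They are all-grade incidences. Related Grade 2 events and all Grade 3-4 events would still be entered under 10.62, so these rates are not the share lost.

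**Conclusion.** The inconsistency is real and should be resolved. Section 10.62 conflicts with 10.82/10.88 over what enters the case report form, and data collected under 10.62 alone cannot supply the all-cause summary in 16.324 below Grade 3 for unsolicited terms. The possible understatement is 0 to about 6 of 52 patients for diarrhea and likewise for nausea, or roughly 2 to 3 patients per term in each cohort at the upper end, plus any related Grade 1 events. This rests on the monotherapy rates applying to the combination and on unrelated events being Grade 2 or lower.

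It would be wrong to read this as a weakness in serious-toxicity monitoring. Solicited terms, Grade 3-4 events and deaths within 30 days are collected whatever their attribution, and the stopping rule in 16.352 uses Grade 4 or higher non-hematologic events. Nor does the plan give the summary a title that could be called false. The issue is the unstated scope of the data behind it.

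**What to change.** Reconcile 10.62 with 10.82 and 10.88 so that one rule governs entry in the case report forms, and state in 16.324 the grades and attributions that the summary covers.

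- **If the wider rule is chosen:** amend 10.62 to take all grades whatever the attribution. The cost is some data entry that 10.88 already requires, and 16.324 can keep its all-cause wording.
- **If the 10.62 rule is kept:** bring the entry requirement in 10.82/10.88 into line with it. In 16.324, limit the all-cause summary to solicited terms and Grade 3 or higher, and present unsolicited Grade 2 events separately, labeled as treatment-related only. The cost is a few sentences and a relabeled table.

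Neither option changes the sample size, the primary analysis or the stopping rule.

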6.7 Baseline symptoms

All required baseline symptoms (see [Section 10.6](#)) must be documented and graded.

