10.82 Management of Safety Data

The study has been designated as an interventional study. As such, all adverse events for Janssen Medicinal Products regardless of causality and special situations excluding those from subjects not exposed to a Janssen Medicinal Product and product quality complaints with or without an adverse event as described in this protocol will be reported from the time a subject has signed and dated an Informed Consent Form (ICF) until completion of the subject's last study-related procedure. Serious adverse events will be reported for 30 days after the last dose of study drug.

For the purposes of this study, the J&J medicinal product is: DARZALEX®™ (daratumumab) FASPRO™ (daratumumab-SC)

For the purposes of this study, the J&J medicinal product is:

IMBRUVICA® (Ibrutinib)

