Appendix V Grading Scale for Hematologic Toxicity in CLL Studies

Non Hematologic Toxicity will be scored using NCI CTCAE (version 5.0) for toxicity and adverse event reporting.

Hematologic toxicity will be assessed using IWCLL/Hallek December 2008⁶ Grading scale for hematologic toxicity in CLL studies

Grade *	T Decrease in platelets or Hb (nadir) from pretreatment value, %	+	Absolute neutrophil count/ μ L (nadir)
0	No change to 10%		≥ 2000
1	11%-24%		≥ 1500 and < 2000
2	25%-49%		≥ 1000 and < 1500
3	50%-74%		≥ 500 and < 1000
4	$\geq 75\%$		< 500

* Grades: 1, mild; 2, moderate; 3, severe; 4, life-threatening; 5, fatal. Death occurring as a result of toxicity at any level of decrease from pretreatment will be recorded as grade 5.

† Platelet counts must be below normal levels for grades 1 to 4. If, the platelet count is $< 20 \times 10^9/L$ ($20\ 000/\mu L$) at any level of decrease, this will be considered grade 4 toxicity unless a severe or life-threatening decrease in the initial platelet count (eg, $20 \times 10^9/L$ [$20\ 000/\mu L$]) was present pretreatment. In this case, the patient will not be evaluable for toxicity referable to platelet counts.

‡ Hb levels must be below normal levels for grades 1 to 4. Baseline and subsequent Hb determinations must be performed before any given transfusions. The use of erythropoietin is irrelevant for the grading of toxicity but should be documented.

§ If the absolute neutrophil count (ANC) reaches $< 1 \times 10^9/L$ ($1000/\mu L$), it should be judged to be grade 3 toxicity. Other decreases in the white blood cell count or in circulating neutrophils are not to be considered because a decrease in the white blood cell count is a desired therapeutic endpoint. A gradual decrease in granulocytes is not a reliable index in CLL for stepwise grading of toxicity. If the ANC was $< 1 \times 10^9/L$ ($1000/\mu L$) before therapy, then the patient will not be evaluable for toxicity referable to the ANC. The use of growth factors such as G-CSF is not relevant to the grading of toxicity but should be documented.

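### For seven non-hematologic terms graded at entry, the toxicity table takes the maximum grade without comparing it with the baseline grade

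*Combined protocol and SAP*

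**What the plan says.** Section 16.324 (Adverse Events) defines the toxicity summary for secondary goals 2.24 and 2.28: "The maximum grade for each type of adverse event, regardless of causality, will be recorded and reported for each patient". Frequency tables follow. Recording ends 30 days after the last day of study drug. The section gives no start date, no definition of a treatment-emergent event and no comparison with baseline.

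Section 10.61 sets up the data: "Pretreatment symptoms/conditions to be graded at baseline and adverse events to be graded at each evaluation". Seven non-hematologic terms are marked for both baseline and each evaluation: atrial fibrillation, fatigue, hemorrhage, bruising, maculo-papular rash, arthralgia and hypertension. Section 6.7 makes this compulsory: baseline symptoms "must be documented and graded".

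The two blood counts are handled differently. Section 16.324 states: "Platelets and hemoglobin will be graded according to the Grading Scale for Hematologic Adverse Events in CLL Studies in Appendix V". The metric in Appendix V is "Decrease in platelets or Hb (nadir) from pretreatment value", and a footnote to 10.61 says who applies it and when: "Grading will be performed by the study statisticians at the time of analysis based on the CLL toxicity grading scale".

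**The concern.** The trial collects a baseline grade for seven terms and the analysis plan then gives it no role. A patient with Grade 1 fatigue at entry and at every visit has a maximum grade of 1, and one with Grade 2 hypertension throughout has a maximum grade of 2. The literal rule tabulates both, although nothing changed on treatment.

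Each cohort is a single arm, so no control group shows the background rate. Cohort 1 is the more exposed. Under 3.14 its patients have stopped a BTK inhibitor (for almost any reason, including most toxicity) or are still taking one. Section 7.0 lets some continue it until study treatment starts. Section 1.2 itself describes bleeding, rash, arthralgia, hypertension and atrial fibrillation with ibrutinib. Effects of the earlier drug that are present at entry could appear as on-study events, and Cohort 1 could look more toxic than Cohort 2 for that reason alone.

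Two uses of the table would suffer. Section 16.23 brings toxicity into any decision to terminate. A reader will also compare the rates with the ibrutinib experience in 1.2, which is given as treatment-emergent rates (fatigue 28.6% in the pooled monotherapy studies, 27.7% in the randomized Phase 3 study). A raw maximum-grade rate is a different quantity.

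**Working it through.** **1. Text check.** Three treatments of baseline stand side by side.

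- Platelets and hemoglobin: graded as a percentage fall from the pretreatment value. For example, an assumed hemoglobin of 9.0 g/dL falling to 8.5 g/dL is (9.0 − 8.5)/9.0 = 5.6%, which is Appendix V grade 0. Anemia present at entry is therefore not counted on this scale.
- The seven terms above: graded at baseline and on study, with no rule linking the two.
- Terms outside the 10.61 list: under 10.62, Grade 2 events are submitted only if at least possibly related, and Grade 3 and 4 events whatever the attribution. Most low-grade symptoms present at entry are therefore filtered out.

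The gap is confined to the seven terms.

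**2. Size.** The plan states no figure to reproduce and gives no baseline prevalence, so the inputs are assumptions:

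- b = share of patients with the symptom at baseline, assumed to persist on treatment
- n = share of those without it who develop it
- w = share of those with it who worsen

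Under the literal rule, the share reported at any grade is b + (1 − b)n. A table of new or worsened events would show (1 − b)n + bw. The difference is b(1 − w).

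With n = 20%:

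| b | Literal rule | New or worse, w = 0 | New or worse, w = n |
|---|---|---|---|
| 10% | 10 + 18 = 28% | 18% | 18 + 2 = 20% |
| 30% | 30 + 14 = 44% | 14% | 14 + 6 = 20% |
| 50% | 50 + 10 = 60% | 10% | 10 + 10 = 20% |

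Cohort sizes are from 16.12. At b = 30%, 44% is 9.7 of 22 patients in Cohort 1, against 3.1 (w = 0) or 4.4 (w = n). In Cohort 2 it is 11.4 of 26, against 3.6 or 5.2.

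**3. When does baseline dominate?** When b > (1 − b)n, that is, b > n/(1 + n). For n = 20% the threshold is 0.20/1.20 = 16.7%; for n = 10% it is 0.10/1.10 = 9.1%. At b = 10% and n = 20%, new events are 18 of the 28 points (64%), so baseline does not dominate.

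**4. Comparison with the cited rate.** Suppose the combination has exactly the cited treatment-emergent fatigue rate of 28.6%, whether or not fatigue was present at entry (w = n), and assume b = 30%. The literal table shows 1 − 0.70 × 0.714 = 50.0%, or 11.0 of 22 patients, where a like-for-like table shows 28.6%, or 6.3 of 22.

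**The case against.** The strongest reply is that the plan is silent here, not wrong. Section 10.61 names pretreatment symptoms and adverse events separately, and section 10.0 ties an adverse event to the use of a drug. A careful analyst could leave out unchanged symptoms without breaching 16.324. That stands as a limit on the claim: the inflation follows from a literal reading, not from an instruction to count such symptoms. But two analysts could then build different tables from the same data, which is a reason to write the rule down.

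The table is also descriptive and makes no claim of cause. It can over-report but does not hide toxicity. The stopping rule in 16.352 filters on attribution and on Grade 4 or higher, so it does not depend on this table. All of that stands, and it limits the consequence to description and comparison.

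A rule that counts only grades above baseline would have its own fault. Atrial fibrillation, bleeding, rash or bruising that resolved and came back at the same grade would drop out. This stands, and the fix allows for it.

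Three stronger readings are tempting and are not supported:

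- A reader might infer that the toxicity analysis never uses baseline. It does, for platelets and hemoglobin. CTCAE grades for these are recorded as well, but 16.324 names Appendix V for the analysis.
- A reader might infer from 10.82, which starts reporting at consent, that events before the first dose enter the table. That section governs reporting to the drug supplier and does not set the window for 16.324.
- A reader might infer that the table would mostly show symptoms present at entry. Step 3 of the working shows that this depends on b and n.

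**Conclusion.** The point holds for the seven non-hematologic terms graded both at baseline and at each evaluation. As written, 16.324 allows an unchanged symptom from before treatment to be reported in the toxicity table, and the exposure is greatest in Cohort 1. No decision rule or stated design figure changes.

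The size is unknown. If symptoms at entry persist, the excess over a new-or-worsened table is b(1 − w). With n = 20% and w between 0 and n, that is 8 to 10 percentage points at b = 10% and 24 to 30 points at b = 30%. It shrinks if symptoms present at entry clear and stay clear on treatment. This is a correction worth making before analysis, not a flaw in the design.

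**What to change.** Add to 16.324, for atrial fibrillation, fatigue, hemorrhage, bruising, maculo-papular rash, arthralgia and hypertension:

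> Events from first dose to 30 days after last dose are tabulated when they are new, worse than the baseline grade, or recur after documented resolution; the maximum such grade is reported. The unadjusted maximum-grade table is presented alongside, with the baseline grade shown.

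Platelets and hemoglobin stay on Appendix V.

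The cost is one derived variable per term and a second table. The grades are already collected at baseline and at each evaluation, and keeping the unadjusted table means nothing is lost. The downside is that the adjusted table will show fewer low-grade events, and the recurrence criterion depends on resolution having been documented.
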